7.2.2. Adverse Event Attribution

An expected adverse event is an event previously known or anticipated to result from participation in the research study or any underlying disease, disorder, or condition of the subject. The event is usually listed in the Investigator Brochure, consent form or research protocol.

An unexpected adverse event is an adverse event not previously known or anticipated to result from the research study or any underlying disease, disorder, or condition of the subject.

Attribution is the relationship between an adverse event or serious adverse event and the study treatment. For the purposes of this study, adverse events may be differentiated as a radiation-induced AE or an immune-related AE (irAE). Attribution will be assigned as follows:

- Definite – The AE is clearly related to the study drug.
- Probable – The AE is likely related to the study drug.
- Possible – The AE may be related to the study drug.
- Unlikely – The AE is doubtfully related to the study drug.
- Unrelated – The AE is clearly NOT related to the study drug.

Protocol must specify if attribution is required for individual components of the treatment regimen or the treatment regimen as a whole.

7.3. Adverse Event Reporting Procedures

All patients will be evaluable for toxicity from the time of their first treatment with immune therapy. It is the responsibility of all investigators to assess AEs during the subject's participation in the study. Subjects will be followed for **30** days after treatment has stopped or until an alternative systemic therapy has been started or until death, whichever comes first. Each AE should be followed until resolution, stabilization, or until it has been determined that the study treatment or participation is not the cause.

Adverse events that occur after the subject has started immune therapy must be documented in the study database/case report forms (OnCore or other PRMC approved database), subject's medical records, and as required per additional institutional standards. Source documentation must be available to support all reported adverse events.

A laboratory test abnormality considered clinically relevant (e.g., causing the subject to withdraw from the study), requiring treatment or causing apparent clinical manifestations, or judged relevant by the investigator, should be reported as an adverse event.

This protocol will use the NCI Common Terminology Criteria for Adverse Events (CTCAE) version 4.0 available at <http://ctep.cancer.gov> for adverse event reporting.

7.4. Serious Adverse Event Reporting Procedures

Serious Adverse Events (SAE) requiring expedited reporting within 24 hours will also be reviewed by DSTC at the next scheduled meeting. For immune-related SAE's attributed to FDA approved standard of care immune therapy, FDA MedWatch will be used only for unexpected related events (not on package insert). All serious adverse events due to radiation therapy will be reported into OnCore and internally reviewed. All subsequent SAE documentation will be submitted to the DSTC once available. The DSTC will determine if further action is required.

7.5. SAEs and OnCore

- All SAEs will be entered into OnCore.
- A copy of the SAE form(s) submitted to the sponsor-investigator is also uploaded into Oncore.

7.6. Data Safety and Toxicity Committee

It is the responsibility of each site PI to ensure that ALL SAEs occurring on this trial (internal or external) are reported to the MBRCC DSTC, Data and Safety Toxicity Committee. This submission is simultaneous with their submission to the sponsor and/or other regulatory bodies.

The sponsor-investigator is responsible for submitting an annual report to the DSTC as per MBRCC Data and Safety Monitoring Plan.

7.7. Data and Safety Monitoring Plan (DSMP)

This protocol will adhere to the policies of the Mary Babb Randolph Cancer Center Data and Safety Monitoring Plan in accordance with NCI guidelines.

8. PHARMACEUTICAL INFORMATION

A list of the adverse events and potential risks associated with the investigational or commercial agents administered in this study can be found in Section 7. Immune checkpoint inhibitors that are FDA approved for use in patients with metastatic NSCLC will be acceptable for use concurrently with radiotherapy in this trial.

8.1. Commercial Agent #1

8.1.1. Name of Agent Nivolumab

Other Names: Opdivo

Product description: Nivolumab Injection is a clear to opalescent, colorless to pale yellow liquid; light (few) particulates may be present. The drug product is a sterile, nonpyrogenic, single-use, isotonic aqueous solution formulated in sodium citrate, sodium chloride, mannitol, diethylenetriaminepentacetic acid (pentetic acid) and polysorbate 80 (Tween® 80), pH 6.0.

Solution preparation: Nivolumab injection can be infused undiluted (10 mg/mL) or diluted with 0.9% Sodium Chloride Injection, USP or 5% Dextrose, USP to drug concentrations no less than 0.35 mg/mL. Note: Mix gently. Do not shake.

Compatibility: no incompatibilities between nivolumab and polyvinyl chloride (PVC), nonPVC/non DEHP (di(2-ethylhexyl)phthalate) IV components, or glass bottles have been observed.

Attach a low protein binding filter 0.2-1.2 micron

Storage requirements: Vials of nivolumab injection must be stored at 2°-8°C (36°-46°F) and protected from light, freezing and shaking.

Stability: The administration of undiluted and diluted solutions of nivolumab must be completed within 24 hours of preparation. If not used immediately, the infusion solution may be stored up to 24 hours in a refrigerator at 2°-8°C (36°-46°F) and a maximum of 4 hours of the total 24 hours can be at room temperature (20°-25°C, 68°-77°F) and room light. The maximum 4-hour period under room temperature and room light conditions includes the product administration period.

Route of administration: Nivolumab injection is to be administered as a 30 minute IV infusion through a 0.2 micron to 1.2 micron pore size, low-protein binding polyethersulfone membrane in-line filter. DO NOT administer as IV push or bolus injection.

Drug Procurement: Nivolumab is considered standard of care and will be utilized from commercially available supply. Nivolumab is available as 40 mg/4 mL single-dose vial and 100 mg/10 mL single-dose vial.

The cost of this agent will be the subject's responsibility.

Drug Accountability: N/A; this is standard of care treatment.

Drug Destruction: Commercially available supply. Institutional standards apply

8.2. Commercial Agent #2

8.2.1. Name of Agent Pembrolizumab

Other Names: Keytruda

Product description: Pembrolizumab Solution for Infusion is a sterile, non-pyrogenic aqueous solution supplied in single-use Type I glass vial containing 100 mg/4 mL of pembrolizumab (MK-3475). The product is preservative-free solution which is essentially free of extraneous particulates.

Solution preparation: Pembrolizumab infusion solutions should be prepared in **0.9% Sodium Chloride Injection, USP** (normal saline) or regional equivalent or 5% Dextrose

Injection, USP (5% dextrose) or regional equivalent and the final concentration of pembrolizumab in the infusion solutions should be between 1 mg/mL and 10 mg/mL.

Please note, the preferred diluent is 0.9% Sodium Chloride and 5% dextrose is only permissible if normal saline is not available.

Storage requirements: Pembrolizumab Solution for Infusion, 100 mg/ 4 mL vial for Infusion should be stored at refrigerated conditions (2 – 8 °C) and protected from light.

Note: vials should be stored in the original box to ensure the drug product is protected from light.

Stability: Following reconstitution with sterile water for injection, Pembrolizumab infusion solutions should be prepared in **0.9% Sodium Chloride Injection, USP** (normal saline) and the final concentration of pembrolizumab in the infusion solutions should be between 1 mg/mL and 10 mg/mL.

If normal saline is not available, 5% Dextrose Injection, USP or regional equivalent (5% dextrose) is permissible.

Please note, the preferred diluent is 0.9% Sodium Chloride and 5% dextrose is only permissible if normal saline is not available.

Pembrolizumab solutions may be stored at room temperature for a cumulative time of up to 6 hours. This includes room temperature storage of admixture solutions in the IV bags and the duration of infusion

In addition, IV bags may be stored under refrigeration at 2 °C to 8 °C (36 °F to 46 °F) for up to 24 hours. If refrigerated, allow the IV bags to come to room temperature prior to use.

Parenteral drug products should be inspected visually for particulate matter and discoloration prior to administration. Discard the drug product vial if extraneous particulate matter other than translucent to white proteinaceous particles is observed.

Route of administration: Administer infusion solution intravenously over 30 minutes through an intravenous line containing a sterile, non-pyrogenic, low-protein binding 0.2 micron to 5 micron in-line or add-on filter.

Drug Procurement: Pembrolizumab is considered standard of care in this trial and will be utilized from commercially available supply. Pembrolizumab injection (solution): carton containing one 100 mg/4 mL (25 mg/mL), single-use vial

The cost of this agent will be the subject's responsibility.

Drug Accountability: N/A; this is standard of care treatment.

Drug Destruction: Commercially available supply. Institutional standards apply

Other Information:

- **DO NOT USE PEMBROLIZUMAB IF DISCOLORATION IS OBSERVED.**
- **DO NOT SHAKE OR FREEZE THE VIAL(S).**
- **DO NOT ADMINISTER THE PRODUCT AS AN (INTRAVENOUS (IV) PUSH OR BOLUS).**
- **DO NOT COMBINE, DILUTE OR ADMINISTER IT AS AN INFUSION WITH OTHER MEDICINAL PRODUCTS.**
- **DO NOT CO-ADMINISTER OTHER DRUGS THROUGH THE SAME INFUSION LINE.**
- Parenteral drug products should be inspected visually for particulate matter and discoloration prior to administration. Discard the drug product vial if extraneous particulate matter other than translucent to white proteinaceous particles is observed.

8.3. Commercial Agent #3

8.3.1. Name of Agent Atezolizumab

Other Names: Tecentriq

Product description: Atezolizumab Injection is a colorless to slightly yellow solution. The drug product is a sterile, nonpyrogenic, single-use, isotonic aqueous solution formulated in glacial acetic acid, L-histidine, sucrose, polysorbate 20. pH 5.8.

Solution preparation: Withdraw 20 mL of atezolizumab from the vial; dilute into a 250 mL bag containing 0.9% Sodium Chloride Injection, USP. Dilute dose in NS only; gently invert to mix without shaking. Discard vial if solution is cloudy, is discolored, or contains visible particles.

Compatibility: Use infusion bag made of polyvinyl chloride (PVC), polyethylene (PE), or polyolefin (PO).

Storage requirements: Diluted infusion solution may exist at room temperature for no more than 6 hours (including infusion time), or under refrigeration (2 to 8°C or 36 to 46°F) for no more than 24 hours. Protect from light. Do not shake. Do not freeze.

Stability: The administration of undiluted and diluted solutions of atezolizumab must be completed within 24 hours of preparation. If not used immediately, the infusion solution may be stored up to 24 hours in a refrigerator at 2° to 8°C (36° to 46°F) and a maximum of 6 hours of the total 24 hours can be at room temperature (20° to 25°C, 68° to 77°F) and room light. The maximum 6-hour period under room temperature and room light conditions includes the product administration period.

Route of administration: Atezolizumab injection is to be administered as a 60 minute infusion for the initial dose. If first dose is well tolerated, may infuse subsequent doses over 30 minutes. Infuse with or without a 0.2- to 0.22-micron sterile, non-pyrogenic, low-protein binding in-line filter. Do not administer as an IV push or bolus. Do not administer other medications at the same time through the same IV line. Monitor for infusion reactions. Atezolizumab is compatible in NS.

Drug Procurement: Atezolizumab will be obtained from commercially available supply. Atezolizumab is available as a 60 mg/1 mL (1200 mg/20 mL) PF single dose vial.

The cost of this agent will be the subject's responsibility.

Drug Accountability: FDA labelled indication non-small cell lung cancer (NSCLC), Metastatic, with progression during or after platinum-based chemotherapy; patients with ALK or EGFR genomic tumor aberrations should have disease progression on FDA-approved therapy for these aberrations prior to receiving atezolizumab. Pre-clinical and clinical studies have established a safety and efficacy profile for this drug beyond that of its FDA labelled indication.

Drug Destruction: Commercially available supply. Institutional standards apply.

9. CORRELATIVE STUDIES

9.1. Correlative Study #1

Use flow cytometry to characterize levels of circulating CD4+, CD8+ and Treg T-cell subsets, as well as iNOS+/CD80+ macrophages in peripheral blood samples.

9.1.1. Background

Preclinical data suggests that immune checkpoint inhibitors increase the quantity of the activated cytotoxic T-cell subpopulation, with a higher CD8/Treg ratio correlating with more robust immune activation.²⁸⁻²⁹ Additionally, M1/TH1 pro-inflammatory iNOS+/CD80+ macrophages may also be recruited to a tumor and involved in cell-killing in this clinical context.³⁰⁻³¹

9.1.2. Rationale for Analysis

Biomarkers predictive of response to immune therapy are currently not well developed. Levels of circulating immune cells before and during therapy have the potential to help

better determine which patients will benefit from therapy. The data from these correlative studies will be used as part of a univariate and multivariate logistic regression model to assess the association between response to treatment and several variables related to the radiotherapy, tumor, and patient characteristics.

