9.1.3. Collection of Specimens

After consenting patients, peripheral blood samples will be collected at baseline before initiation of treatment and at the time of any change in response status as assessed on follow-up imaging studies. All attempts will be made to draw the blood with currently scheduled venipuncture, but it will also be permissible to draw specifically for this study if necessary.

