9.2.2. Rationale for Analysis

As above, biomarkers predictive of response to immune therapy are currently not well developed. Levels of circulating cytokines and chemokines for T-cells and macrophages before and during therapy have the potential to help better determine which patients will benefit from therapy. The data from these correlative studies will be used as part of a univariate and multivariate logistic regression model to assess the association between

response to treatment and several variables related to the radiotherapy, tumor, and patient characteristics

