⁶Serum chemistries include sodium, potassium, chloride, bicarbonate, BUN, creatinine, glucose, calcium, magnesium, phosphorous, albumin

⁷Serum liver function tests include alkaline phosphatase, total bilirubin, total protein, SGOT [AST], SGPT [ALT]

⁸Only for women of childbearing potential (within 14 days of registration)

⁹Only for patients with diabetes mellitus

¹⁰In patients with contrast allergy a short course of steroids may be given as needed. In patients with poor kidney function in whom contrast is contraindicated a non-contrast imaging study is permissible.

¹¹Please refer to protocol section 9 for details. The initial research blood sample may be drawn anytime between signing the consent and the first immune therapy treatment.

¹²Record all past and current administrations of immune therapy (sections 5.2 and 6.2), including date and dose of each administration.

¹³Record all past and current administrations of radiation therapy (sections 5.1, 5.3, and 6.1), including for each course: the start and end date, total dose, dose per fraction, number of fractions, and location of treated lesion.

¹⁴Survival assessment may be carried out via chart review or phone call only.

¹⁵A window of \pm 14 days around the standard time point every 3 months is allowed as necessary

¹⁶A minimum of one scan every 4 months is required, however, scans may be completed at more frequent intervals as clinically indicated.

¹⁷Performed in coordination with imaging studies, at baseline prior to treatment, and thereafter only for a change in extracranial response on follow-up imaging. The blood will be drawn within 30 days of any imaging study showing a change in extracranial response status.

¹⁸Optional rebiopsy of an accessible non-irradiated tumor may be obtained at the treating physicians' discretion if it is deemed clinically warranted and safe to perform, for diagnostic purpose in order to confirm progression of disease and underlying histopathology. If indicated, it should be carried out within 30 days of the confirmatory imaging study showing disease progression, and prior to initiating any further systemic therapy.

¹⁹AEs and SAEs will be collected on a continuous basis starting with the first cycle of immune therapy. Both AEs and SAEs will be collected up until 30 days after the last dose of immune therapy or until the patient begins a new cancer-directed therapy, or death, whichever comes first.

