13.2. Sample Size/Accrual Rate

The primary analysis will be for patients enrolled at time-points (A) and (B) above, whereas patients enrolled at time-point (C) will be included in observational analysis only (see section 3.1). The primary endpoint of this study is the overall response rate (complete + partial response) and the efficacy will be assessed using the Simon's two-stage Minmax design. A sample size of 33 patients is chosen to differentiate between the response rate of 20% and 40% with 80% power at a significance level of 0.05. In particular, 18 patients will be enrolled at the first stage. If 15 or more of the first 18 patients have disease progression prior to any response, the trial will be terminated; otherwise an additional 15 patients will be treated for a total of 33 patients. In the final data analysis, if 10 or fewer patients respond among 33 patients, the treatment will be concluded ineffective. The probability of early termination due to futility is 0.72.

For correlative study between biomarkers and response, this sample size will have at least 80% power to detect a 50% change/difference on biomarker data between response and non-response groups using a two-sided two-sample t-test at 0.05 significance level, assuming that the response rate is 35% or higher and the coefficient of variation (CV) of biomarkers is 0.45.

Approximately 100 patients with metastatic NSCLC are diagnosed and treated each year at our institution, many of whom will be candidates for immune checkpoint therapy. As such, we expect to accrue 3 patients per month to this trial for an estimated accrual period of one year. The full estimated duration of the study is two years.

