13.3. Methods for Analysis

Data will be summarized with respect to baseline characteristics and safety measurements using descriptive statistics (quantitative data) and contingency tables (qualitative data). The safety analysis will consist of AE summaries (frequency tables based on CTCAE grades) and laboratory abnormalities summary. For the primary endpoint, the response rate and its 95% confidence interval will be estimated with a binomial distribution. Univariate and multivariate logistic regression model will be used to assess the association between response and several radiotherapy variables (biologic effective dose,

number of lesions treated, sequence of radiation and immune therapy), tumor variables (irradiated tumor site, size, growth rate, histology, PD-L1 status, local response, extent of prior chemotherapy use, and biologic correlates), and patient variables (age, smoking status, and other factors associated with secondary immunodeficiency). A predictive nomogram for response will be developed based on the outcome of the multivariate analysis. In the data analysis on the secondary endpoints, the Kaplan-Meier method will be used to estimate overall survival and progression-free survival. Wilcoxon signed-rank test for paired data will be used to assess the change of quality of life scores between two visits. Since the lung cancer score (LCS) of the FACT-L focuses on lung cancer symptoms, this will be used for the primary QOL endpoint; however, the more general subscales of physical and functional well-being on the Trial Outcome Index (FACT-TOI) will also be collected. A difference of 3 LCS points will be considered clinically significant.¹²⁻¹³ Where applicable, comparison will be made to previous randomized trials assessing immune checkpoint inhibitors alone in a comparable patient population.

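### Marker values drawn because response status changed are not kept out of the logistic model for response or the predictive nomogram (Sections 9.1.2, 9.2.2 and 13.3)

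*Combined protocol and SAP*

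**What the plan says.** **What enters the model.** Section 9.1.2 says "Levels of circulating immune cells before and during therapy have the potential to help" show which patients will benefit. Section 9.2.2 makes the same claim for "Levels of circulating cytokines and chemokines for T-cells and macrophages before and during therapy". Both then state: "The data from these correlative studies will be used as part of a univariate and multivariate logistic regression model", with response to treatment as the outcome. Section 13.3 lists biologic correlates among the covariates without a time point and adds: "A predictive nomogram for response will be developed based on the outcome of the multivariate analysis". Section 1.2 gives the aim as finding factors predictive of response. No section restricts the model to baseline samples, sets a landmark, or separates baseline from later values.

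**When blood is drawn.** Sections 9.1.3 and 9.2.3 give two occasions: baseline, and "at the time of any change in response status as assessed on follow-up imaging studies". Footnote 17 of the study calendar (10.2) confirms that after baseline a change in extracranial response is the only trigger, and adds: "The blood will be drawn within 30 days of any imaging study showing a change in extracranial response status". The synopsis and Section 1.3 list a further sample at the first follow-up imaging, separate from the change-triggered ones and not conditional on response.

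**The concern.** A predictor has to be measured before the outcome it predicts. Under Section 9 and the calendar, the only on-treatment value exists because a scan has already shown the outcome moving. If the marker changes because tumor shrank or grew, the logistic model will show an association even when the marker carries no information in advance. A nomogram that needs such a value cannot be used until response status is already known, and its apparent discrimination is inflated.

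Two further problems follow from the same trigger. Patients who stay stable never meet it, so whether the covariate is missing depends on the outcome. And time on treatment at the draw is set by when status changes, so it can differ between outcome groups, and a plain time trend in a marker can look like an association with response.

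**Working it through.** The point rests on the order of events. The arithmetic only shows how large the effect could be.

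**1. The sampling statements side by side.**

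| Place | Post-baseline samples | Order relative to response |
|---|---|---|
| 9.1.3, 9.2.3 | on a change in response status | after the change is seen |
| 10.2, footnote 17 | only on such a change, within 30 days of the scan | after the change is seen |
| Synopsis, 1.3 | at first reimaging, plus on a change | first-reimaging sample: before later responses, but not before those first seen on that scan |
| 9.1.2, 9.2.2, 13.3 | none excluded from the model | not addressed |

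**2. The plan's own biomarker power figure.** Section 13.2: "A sample size of 33 patients is chosen", with "at least 80% power to detect a 50% change/difference on biomarker data between response and non-response groups", two-sided t-test at 0.05, response rate 35% or higher, CV 0.45. Then 33 × 0.35 = 11.55, so about 12 versus 21. Set the reference mean to 1, the difference to 0.5 and the common SD to 0.45; the standardized difference is 0.5/0.45 = 1.11.

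Noncentrality = 0.5 / (0.45 × √(1/12 + 1/21)) = 0.5/0.163 = 3.07; 31 df; critical t 2.04; power 0.845. For 11 versus 22 the noncentrality is 3.01 and power 0.830. With a common SD, the stated figure of at least 80% reproduces.

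**3. The same formula applied to a marker that predicts nothing.** Assume no baseline difference and a shift δ in responders that occurs only because they responded. The t-test stands in for the univariate logistic test. AUC = Φ(δ / (0.45 × √2)).

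| Value used | δ | Probability of significance | AUC |
|---|---|---|---|
| Baseline | 0 | 0.05 | 0.50 |
| Post-response | 0.25 (0.56 SD) | 0.32 | Φ(0.393) = 0.65 |
| Post-response | 0.50 (1.11 SD) | 0.845 | Φ(0.786) = 0.78 |

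Simulation gives 0.32 and 0.85 for the two shifts and 0.05 for baseline.

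**4. Allowing for stable patients without a sample.** Step 3 gives all 33 patients an on-treatment value, which the Section 9 schedule does not. With δ = 0.50 and 12 responders against 15, 10 or 5 sampled non-responders (assumed counts), the probability is 0.79, 0.69 or 0.50. Those sampled non-responders would mostly be at progression, and their values may have shifted too. The documents give no basis for saying in which direction.

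**5. If the first-reimaging sample is drawn and used for everyone.** Suppose only some of the 12 responders are already responding at that scan (assumed fractions; δ = 0.50; 21 non-responders unshifted).

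| Already responding | Probability of significance (simulated) | AUC |
|---|---|---|
| 9 of 12 | about 0.57 | 0.75 × 0.784 + 0.25 × 0.50 = 0.71 |
| 6 of 12 | about 0.28 | 0.50 × 0.784 + 0.50 × 0.50 = 0.64 |

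The distortion shrinks but does not vanish unless patients already responding or progressed at that scan are set aside.

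**The case against.** A reader might infer that every on-treatment sample is drawn only after, and because, response has changed, and that the plan therefore specifies a model with time reversed. The documents do not support that.

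- The synopsis and Section 1.3 schedule a first-reimaging sample whatever the response. Section 11.1.2 notes that responses can take months to appear, so this sample can precede a later response and could support a valid landmark analysis.
- Confirmed response needs two observations at least 4 weeks apart (11.2), so a triggered draw can precede confirmation, although shrinkage is already visible.
- Triggered draws also follow progression, so they are not all a consequence of response.
- Section 9.1.2 speaks of association, 13.1 of markers in relation to response, and 2.5 says the triggered samples are meant to relate treatment's biological effects to response. That is close to descriptive use.
- The synopsis calls the response-correlation analysis exploratory (Section 1.2 places it under secondary objectives), and the primary endpoint is untouched.

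All of this stands and limits the claim. It does not remove it. Section 9 and the calendar, which govern collection, omit the first-reimaging sample. Even where that sample is drawn, it does not precede a response first seen on the same scan. The predictive purpose is explicit in 1.2 and 13.3, and nothing excludes the triggered values. A value drawn after progression is no more use for forecasting response than one drawn after shrinkage.

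**Conclusion.** The concern holds in this form: the plan lets marker values that follow a change in response status enter the response model and the nomogram, and its own sections disagree on whether any on-treatment sample is independent of response. It leaves the covariate's time point open rather than prescribing the wrong one. Baseline values also feed the model, and for them the order is correct.

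The illustrative probabilities run from 0.28 to 0.85 across the cases shown, against 0.05 for a baseline value. They rest on assumed shifts, an assumed 12 responders, and assumed numbers sampled or already responding. They must not be read as this trial's false-positive rate, because the documents give no size or direction for any marker change after response or progression. The conclusion rests on timing and would stand without them.

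This should be corrected before the correlative analysis. It does not affect the primary response rate or the two-stage rule.

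**What to change.** 1. Reconcile the sampling schedule in the synopsis and Section 1.3 with 9.1.3, 9.2.3 and calendar footnote 17.
2. In 9.1.2, 9.2.2 and 13.3, admit only pre-treatment marker values to the logistic models for response and to the nomogram. If the first-reimaging sample is kept, use it only in a landmark analysis of patients who have neither responded nor progressed at that scan.
3. Report change-triggered samples descriptively, as change from baseline by response group with time since cycle 1 shown, and label them as describing response rather than predicting it.
4. Leave the other post-baseline covariates listed in 13.3 out of the nomogram: local response, and number of lesions treated, which depends on response under 5.3. Otherwise it still cannot be used before treatment.

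Cost: wording only, with no samples beyond those the documents already mention. Power for the baseline comparison stays at 0.845 (12 versus 21) if all 33 patients consent to blood sampling. The price is fewer candidate predictors and, if a landmark analysis is chosen, a smaller analysis set.
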